9.2.4 Per-Protocol Analysis Set (PPS)

The PPS analysis set excludes subjects from the FAS population that may substantially affect the results of the primary efficacy analysis. The PPS population will be used for a sensitivity analysis for primary and key secondary efficacy endpoints.

Determination of the subjects excluded from the PPS will be made prior to unblinding treatment codes of the database and documented in a separate report.

9.3 Primary Estimand, Intercurrent Events, and Estimation

Primary Objective and Population: The primary objective is to compare the efficacy of intranasal administration of twice-daily doses of 186 and 372 µg of OPN-375 (fluticasone propionate) with placebo in subjects with documented CRS without nasal polyps.

9.3.1 Co-primary Endpoints

- Change from baseline to the end of Week 4 in 7-day average instantaneous AM CSNS (evaluation of symptom severity immediately preceding the time of scoring)
 - nasal congestion
 - nasal discharge (anterior and/or posterior)
 - facial pain or pressure sensation

The baseline CSNS will be the average of the CSNS over the last 7 days of the placebo run-in period prior to randomization. The CSNS at Week 4 will be the average of the CSNS over the 7 days prior to Day 28.

AND

- The change from baseline to Week 24/ET in the APOV in the ethmoid and maxillary sinuses (APOV is the average percentage of volume opacified across both maxillary and ethmoid sinuses (all 4 sinuses) at each timepoint)

9.3.2 Potential Intercurrent Events

The potential intercurrent events are as follows:

1. Need for systemic corticosteroids for CRS exacerbation or worsening of CRS nasal/sinus symptoms
2. Need for nasal surgery
3. Discontinuation from study treatment

9.3.3 Primary Estimand

The primary efficacy estimand is the difference between each active treatment of twice-daily doses of 186 µg and 372 µg of OPN-375 and placebo for each of the co-primary endpoints.

For the primary estimand, intercurrent events will be addressed as follows:

1. Systemic corticosteroids use for CRS exacerbation or worsening of CRS nasal/sinus symptoms: a composite strategy will be employed with a poor score assigned to this event.

For CSNS, a value of '9' will be assigned. For APOV, a poor score is defined as follows: for a subject with a baseline APOV $\geq 75\%$, a value of '100%' will be assigned; if baseline APOV $< 75\%$, a poor score is defined as baseline APOV + 25%. Further detail regarding the definition of a poor score and the handling of a missing within-instrument data in these endpoints is provided in the SAP.

Systemic corticosteroid use for other indications will be considered a treatment and study discontinuation event (Reference criteria 3).

2. Nasal surgery: composite strategy with worst scores assigned as above.
3. Treatment Discontinuation: treatment policy strategy; subjects may continue in the study until one of the following three mutually exclusive outcomes:
 - a) Subject completes Week 24/ET CT scan. In the absence of an intercurrent event (systemic corticosteroids, nasal surgery) use the endpoint value;
 - b) An intercurrent event (systemic corticosteroids for CRS exacerbation or worsening of CRS nasal/sinus symptoms, nasal surgery) occurs: Use composite strategy and assign worse score as described above (reference criteria 1, 2);
 - c) Subject discontinues the study. Missing data due to study discontinuation following treatment discontinuation will be imputed; further detail on the imputation method is provided in the estimation section for each of the co-primary endpoints.

9.3.4 Estimator and Estimation Method – Primary Analysis

Estimator and estimation method (CSNS): For the co-primary endpoint CSNS, the estimator is the mean difference between treatments (active versus placebo) in change from baseline to the end of Week 4 in the 7-day average total CSNS (instantaneous AM). Estimation is based on a mixed model for repeated measures (MMRM) where changes from baseline to Weeks 2, 4 in the 7-day average total CSNS (instantaneous AM), respectively, are the repeated measures. The MMRM model will employ Restricted Maximum Likelihood (REML) for parameter estimation and the Kenward-Roger method for calculating the denominator degrees of freedom. An unstructured covariance matrix will be used to estimate within-subject error. For the treatment policy estimand, (reference [Section 9.3.3](#), criteria 3c), missing data due to study discontinuation will be estimated within the MMRM model under the assumption that the missing data are missing at random (MAR) and that early discontinuation from the study (prior to Week 4) is unlikely to reflect a treatment effect.

The MMRM model will include categorical effects for previous sinus surgery (Y,N), treatment (OPN-375 186 µg, OPN-375 372 µg, placebo), week (2, 4) treatment-by-week interaction, and the continuous covariate baseline 7-day average total CSNS (instantaneous AM) with baseline-by-week interaction.

Estimator and estimation method (APOV): For the co-primary endpoint APOV, the estimator is the mean difference between treatments (active versus placebo) in the change from baseline to Week 24/ET APOV. Estimation is based on an ANCOVA model including categorical effects for previous sinus surgery (Y,N), treatment (OPN-375 186 µg, OPN-375 372 µg, placebo), and baseline APOV.

For the treatment policy estimand, (reference [Section 9.3.3](#), criteria 3,c), missing data due to study discontinuation will be imputed with a pattern mixture model (PMM) multiple imputation (MI) using the Jump-to-Control (J2C) method. The PMM assumes that the missing data at Week 24/ET on the control arm (placebo) is MAR, and the missing data on the active treatment arms have the profile of the control arm at Week 24/ET.

Multiple imputation using a PMM with J2C method will be conducted using the sequential modeling method as described in ([O’Kelly et al, 2014](#)). Further detail on the MI implementation, and statistical analysis and inference is provided in the SAP.

9.3.5 Supplementary Analysis

A supplementary analysis of the primary estimand will be performed.

Supplementary estimand: A supplementary efficacy estimand is the difference between each active treatment of twice-daily doses of 186 µg and 372 µg of OPN-375 and placebo in each of the co-primary endpoints, irrespective of systemic corticosteroid use.

That is, for the supplemental estimand, intercurrent events will be addressed as follows:

1. Systemic corticosteroids use for all indications: treatment policy strategy; consider outcomes irrespective of systemic corticosteroid use; subjects may continue in the study until one of the following two mutually exclusive outcomes:
 - a. Subject completes the study, use the endpoint value;
 - b. Subject discontinues the study. Missing data due to study discontinuation following treatment discontinuation will be imputed; further detail on the imputation method is provided in the estimation section for each of the co-primary endpoints.
2. Nasal surgery: composite strategy with worst scores assigned.
3. Treatment discontinuation: composite strategy with poor scores assigned.

The estimator and estimation methods for the co-primary endpoints are the same as for the primary estimand described above.

9.4 Sensitivity Analyses

9.4.1 ANCOVA on Ranked APOV Values

A sensitivity analysis of the primary estimand and APOV co-primary endpoint will be performed based on ranked APOV values after modification of the primary estimand as follows. For the composite strategy, a worst score of 100% is assigned; for the treatment policy strategy, baseline APOV is assigned (BOCF). Baseline and endpoint APOV values are then ranked. Ranked APOV values will be analyzed with an ANCOVA model including categorical effects for previous sinus surgery and treatment. Further detail is provided in the SAP.

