4.3 Withdrawal and Removal of Subjects

Subjects will be informed that they are free to withdraw from study treatment and/or the study at any time at their own request without prejudice to their future medical care, or that they may be withdrawn at any time at the discretion of the investigator or Sponsor for safety, nonadherence to protocol requirements, or administrative reasons (eg, termination of study by Sponsor). Subjects wishing to withdraw from study treatment will be strongly encouraged to continue in the study and have all scheduled study procedures performed.

A subject must be withdrawn from treatment for the following reasons:

- subject becomes pregnant
- A subject's study treatment will be discontinued if the investigator or Sponsor considers it in the subject's best interest to stop treatment, (eg, for safety or significant tolerability reasons such as an AE). Subjects who have one of the following AEs must be withdrawn from study treatment.
- IOP of >21 mm Hg
- nasal septal perforation
- new onset or worsening of cataract

A subject may also be withdrawn from study treatment for the following reasons:

- lack of efficacy
- protocol violation

A subject may be withdrawn from the study for the following reasons:

- withdrawal of consent
- adverse event
- protocol violation that makes it unsafe for the subject to continue in the study
- termination of the study
- lost to follow up
- public health measure
- other

If a subject withdraws from the study after starting study treatment, appropriate follow-up must be conducted wherever possible.

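### The ranked-APOV sensitivity analysis does not list baseline in its model, does not name its response, and does not limit BOCF to missing scans

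*Protocol*

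**What the plan says.** Protocol 9.4.1 sets out a rank-based sensitivity analysis of the APOV co-primary endpoint, run after some changes to the primary estimand. Composite-strategy events receive 100%. Then "for the treatment policy strategy, baseline APOV is assigned (BOCF"). Next, "Baseline and endpoint APOV values are then ranked", and "Ranked APOV values will be analyzed with an ANCOVA model including categorical effects for previous sinus surgery and treatment". The section closes with "Further detail is provided in the SAP".

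Three other places bear on this:

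- **Primary APOV model (Protocol 9.3.4).** The ANCOVA has previous sinus surgery, "treatment (OPN-375 186 µg, OPN-375 372 µg, placebo), and baseline APOV".
- **Treatment policy in the primary estimand (Protocol 9.3.3, item 3).** Item 3a covers subjects whose Week 24/ET scan is done: "In the absence of an intercurrent event (systemic corticosteroids, nasal surgery) use the endpoint value". Item 3c covers subjects who leave the study, and 9.3.4 ties imputation to that case: "missing data due to study discontinuation will be imputed with a pattern mixture model (PMM) multiple imputation (MI) using the Jump-to-Control (J2C) method". SAP Table 5.1, footnote 6a, likewise uses the observed scan.
- **Follow-up after stopping treatment (Protocol 4.3).** Such subjects "will be strongly encouraged to continue in the study and have all scheduled study procedures performed". Protocol 6.5 also asks those who leave the study early to return for a visit that includes a CT scan.

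The CS-3206 SAP does not describe the ranked analysis. Its Introduction makes the CS-3205 SAP the main reference for methods and data handling.

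**The concern.** This is the only rank-based check described for a co-primary endpoint. A programmer working from 9.4.1 alone meets three gaps.

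1. Baseline is ranked and then has no stated use. The model is called an ANCOVA but lists no covariate.
2. The response could be the endpoint rank or the change in rank, and the two have different precision.
3. The BOCF rule names a whole strategy, not missing values. The treatment policy strategy includes 3a subjects, who have an observed scan. The parallel composite rule in the same sentence assigns its score whether or not a scan exists, so the literal reading is a natural one.

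Followed literally, the analysis is less precise than it need be and discards observed data that the primary analysis keeps. A weaker ranked result could then come from the specification and not from any fragility in the primary result.

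**Working it through.** **The plan's own figure.** Protocol 9.1 gives 70 per group, a 9-point difference, SD 17 and two-sided 5%, with 88% power for APOV. The standard error is 17 × √(2/70) = 2.87, and 9/2.87 = 3.13. Power is Φ(3.13 − 1.96) = 87.9%; a noncentral t with 138 df gives 87.5%. The stated 88% reproduces. There is no stated figure for the ranked analysis.

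**Inputs not in the documents.** The baseline-endpoint correlation ρ is assumed, from 0.3 to 0.7. The protocol does not say whether 17 is the SD of change or of the endpoint; the main calculation takes it as the SD of change.

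**Residual SD, unranked.** With endpoint SD s = 17/√(2(1 − ρ)):

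- endpoint response, no baseline: s
- change response, no baseline: s√(2(1 − ρ)) = 17
- with baseline: s√(1 − ρ²)

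Leaving baseline out multiplies the residual variance by 1/(1 − ρ²) for an endpoint response (1.10, 1.33, 1.96 at ρ = 0.3, 0.5, 0.7) and by 2/(1 + ρ) for a change response (1.54, 1.33, 1.18).

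**Power, 70 per arm, 9-point effect, change SD 17.** Unranked values use the normal formula. Ranked values come from 3,000 simulated three-arm trials per setting, with both active arms given the effect and APOV truncated to its range.

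| | ρ = 0.3 | ρ = 0.5 | ρ = 0.7 |
|---|---|---|---|
| Unranked, with baseline | 97% | 95% | 93% |
| Unranked endpoint, no baseline | 96% | 88% | 68% |
| Unranked change, no baseline | 88% | 88% | 88% |
| Ranked, with ranked baseline | 97% | 93% | 89% |
| Endpoint rank, no baseline | 95% | 85% | 65% |
| Change in rank, no baseline | 85% | 83% | 83% |

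The ranked loss is about 2, 8 and 24 points for endpoint rank, and about 12, 10 and 6 points for change in rank.

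**If 17 is the endpoint SD.** A separate simulation of endpoint rank without baseline gives 85%, 87% and 86% at ρ = 0.3, 0.5 and 0.7, close to the planned 88%. The unranked formula with baseline gives 91%, 95% and 99%.

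**Type I error.** Under no effect at ρ = 0.5, simulated rejection without baseline was 5.7% (endpoint rank) and 5.2% (change in rank). The Monte Carlo standard error is √(0.05 × 0.95/3000) = 0.4 points, so neither differs clearly from 5%.

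**Replacing observed scans.** Assumptions: ρ = 0.5, equal treatment discontinuation in all arms, every discontinuer scanned, and the drug effect persisting after discontinuation (2,000 runs per setting). BOCF sets these subjects' change to zero, so the difference shrinks roughly in proportion to the number replaced.

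- 10% discontinuation: 8.9 points becomes 8.0 (8.9 × 0.9 = 8.0). Power with ranked baseline falls from 93% to 90%.
- 20% discontinuation: 8.9 points becomes 7.2 (8.9 × 0.8 = 7.1). Power with ranked baseline falls from 94% to 84%.

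**The case against.** The strongest reply is that 9.4.1 is a short summary that defers to the SAP, and that the SAP of reference, for CS-3205, is not among the documents. It may already name the covariate, the response and the scope of BOCF. The text also leaves room for a benign reading. The listed terms are described as categorical, and ranked baseline is not categorical; ranking baseline within an ANCOVA makes little sense unless it is then used. BOCF is ordinarily a rule for missing values, and 9.3.4 links its own treatment-policy rule to 3c.

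This defeats the stronger reading that a reader might infer: that the plan definitely omits baseline and definitely overwrites every off-treatment scan. The documents do not establish either. Still, 9.3.4 names baseline in a nearly identical sentence, and 9.4.1 has no cross-reference to bring it in, whereas 9.4.2 refers back to 9.3.4 explicitly. Where the protocol means missing data only, it says so. The gap in the text therefore stands.

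A reader might also infer that the analysis fails because it departs from the primary estimand. Departure alone is no defect: 9.4.1 says that it modifies the estimand, and its 100% composite score does so by design. Nor would a disagreement with the primary result be beyond interpretation, because the observed-cases analysis (9.4.2), the tipping point analysis (9.4.3) and the supplementary estimands in SAP Table 5.1 give other views of the same endpoint.

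**Conclusion.** The point holds as a defect of specification in a sensitivity analysis. As written, 9.4.1 ranks baseline without listing it in the model, does not state the response, and does not limit BOCF to missing scans. The last of these, read literally, conflicts with 9.3.3 item 3a and SAP Table 5.1 footnote 6a.

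The precision cost depends on unstated quantities. With a change SD of 17 and correlations from 0.3 to 0.7, it ranges from about 2 to 24 points of power. The figure of 65% should not be read as the power of this analysis: it needs a correlation of 0.7, endpoint rank as response and 17 as the SD of change, all together. Dilution from replaced scans is about 0.9 points of APOV at 10% discontinuation and 1.7 at 20%, if all discontinuers are scanned and their effect persists.

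Type I error is not materially affected. The analysis lies outside the testing hierarchy, and the primary APOV analysis adjusts for baseline and keeps observed scans, so the primary conclusion is not at risk. Priority is low.

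**What to change.** In Protocol 9.4.1 or the CS-3206 SAP:

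1. State that the response is ranked Week 24/ET APOV.
2. Add ranked baseline APOV as a covariate alongside previous sinus surgery and treatment.
3. Assign baseline APOV only when the Week 24/ET APOV is missing (9.3.3 item 3c), and use observed scans after treatment discontinuation as in item 3a.

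If the CS-3205 SAP already says this, a sentence that cites it and brings 9.4.1 into line is enough. The cost is two or three sentences before unblinding, with no new data and no change to the primary analysis.

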9.4.2 Observed Cases Analysis

A sensitivity analysis will be performed for both co-primary endpoints based on the FAS, observed cases population. For each co-primary endpoint, the observed cases population is defined to include all subjects who have an observed value for that endpoint, irrespective of an intercurrent event, and the observed value is used in the analysis. For both co-primary endpoints, the estimator and estimation methods are the same as described in Section 9.3.4, with the exception that in the observed cases population there are no missing data; consequently, no imputation is required.

9.4.3 Tipping Point

If the analysis of both co-primary endpoints is statistically significant, then an additional sensitivity analysis will be performed to determine the smallest constant, δ , when applied to the imputed missing data in the active treatment groups, that will yield a mean treatment difference such that the result using the primary analysis model is no longer statistically significant. The constant δ represents a worsening of treatment values and the smallest value, say δ^* , that yields a non-significant result for the primary analysis is called the “Tipping Point.” Further detail on the Tipping Point analysis is provided in the SAP.

9.5 Key Secondary Efficacy Analyses

The analysis of the following key secondary endpoints are based on pooling the data from Study OPN-FLU-CS-3205 and Study OPN-FLU-CS-3206 (pooled data):

- Change from baseline to Week 4 on CSNS score in subjects who were symptomatic at trial entry despite reported use of an intranasal steroid for treatment of CRS within 30 days of Visit 1 will be analyzed using the same MMRM model described for the co-primary endpoint CSNS and the model will include a categorical effect term for protocol (CS-3205, CS-3206).
- The frequency of acute sinus exacerbations over 24 weeks will be compared between OPN-375 dose groups and placebo using generalized linear model (GLM) for data from the negative binomial distribution that is commonly referred to as the negative binomial (NB) regression model. The NB model will include the same model terms as the primary models; in addition, the model will include a categorical effect for protocol (OPN-FLU-CS-3205, OPN-FLU-CS-3206), and the logarithm of follow-up time as an offset variable. The same model will be used for the pooled analysis of the frequency of acute sinus exacerbations over 24 weeks in the CRS without Nasal Polyps population.

The analysis of the following key secondary endpoints are based on the data from Study OPN-FLU-CS-3206 only:

- change from baseline to the end of Week 4 in four separate cardinal CRS symptoms, as measured by (AM, Instantaneous) CSNS: congestion, facial pain or pressure sensation, nasal discharge (anterior and/or posterior), and sense of smell will be analyzed using the same MMRM model described above.
- The Kaplan-Meier method and log-rank test will be used to estimate and compare the distributions of time to first acute CRS exacerbation between each OPN-375 dose and placebo.

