7.1.2 Information Pertaining to Chronic Rhinosinusitis

Information pertaining to the subject's CRS, including date of initial diagnosis, number of exacerbations in the previous year, prior treatments for the condition (eg, surgery, medication) will be collected.

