5 STATISTICAL METHODS FOR EFFICACY ANALYSES

5.1 Adjustments to the Statistical Models

In Protocol OPN-FLU-CS-3205 randomization was stratified by Nasal Polyp status at baseline (Absent, Present), and Prior Nasal Surgery (Yes, No). All statistical models in the OPN-FLU-CS-3205 SAP include categorical terms for both Nasal Polyp status and Prior Nasal Surgery.

In Protocol OPN-FLU-CS-3206 randomization was stratified only by Prior Nasal Surgery (Yes, No) since the subject population consisted only of subjects without Nasal Polyps at baseline. Therefore, for all statistical models referenced in OPN-FLU-CS-3205 SAP the categorical term for Nasal Polyp status is removed for the analyses of the efficacy endpoints in Protocol OPN-FLU-CS-3206.

There are no other changes to the statistical models or methods in the efficacy analyses of Protocol OPN-FLU-CS-3206.

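### The two pooled 3205+3206 models that include polyp subjects do not name baseline nasal polyp status, a randomisation factor in 3205; adding it is a small, free gain in precision and clarity

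*Protocol*

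**What the plan says.** Protocol 9.5, repeated in the synopsis, defines three pooled key secondary analyses.

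- **Week 4 CSNS in prior intranasal-steroid users.** This "will be analyzed using the same MMRM model described for the co-primary endpoint CSNS and the model will include a categorical effect term for protocol".
- **Exacerbation frequency, all pooled subjects.** This uses a negative binomial model: "The NB model will include the same model terms as the primary models; in addition, the model will include a categorical effect for protocol". Log follow-up time is the offset.
- **Exacerbation frequency, subjects without polyps.** This uses the same negative binomial model.

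Protocol 9.3.4 lists the terms these models inherit: "The MMRM model will include categorical effects for previous sinus surgery (Y,N), treatment", followed by week, treatment-by-week, baseline CSNS and baseline-by-week. The APOV ANCOVA has prior surgery, treatment and baseline APOV. Neither has a polyp term.

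SAP 5.1 gives the background: "In Protocol OPN-FLU-CS-3205 randomization was stratified by Nasal Polyp status at baseline (Absent, Present), and Prior Nasal Surgery (Yes, No"), and all models in the 3205 SAP "include categorical terms for both Nasal Polyp status and Prior Nasal Surgery". Because 3206 enrolled only subjects without polyps, "the categorical term for Nasal Polyp status is removed for the analyses of the efficacy endpoints in Protocol OPN-FLU-CS-3206". SAP 5.1 says nothing about pooled models. SAP 5.2 leaves the full description of the pooled endpoints to the ISE SAP.

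The pooled tests are part of the alpha-controlled sequence. In SAP 5.3.2 they are steps 2 to 4 for 372 µg and steps 11 to 13 for 186 µg.

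**The concern.** The reason for dropping the polyp term in 3206 is that polyp status is constant there. Once 3205's polyp subjects are pooled in, it is no longer constant and the reason lapses. Read literally, Protocol 9.5 then analyses 3205 subjects without one of the two factors they were randomised by, although 3205's own models include it.

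The study effect does not fill the gap. It separates 3206 from 3205, but 3205 contains subjects with and without polyps. Any difference in outcome between those two groups stays in the residual.

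Two things are at stake. One is a little precision in tests that come directly after the primary hypothesis, where a failure stops everything below. The other is clarity: an alpha-controlled test should have one stated model, consistent with the strata used at randomisation.

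**Working it through.** **The plan's own power figure.** Protocol 9.1 gives 70 per group, difference 0.9, SD 1.7, two-sided 5%, 88% power. Check: 0.9 / (1.7 × √(2/70)) − 1.96 = 1.17, and Φ(1.17) = 0.879. With the noncentral t on 138 df the result is 0.875. APOV (9% with SD 17%) has the same ratio and the same result. The figure reproduces, but it concerns the co-primaries only. No power is stated for any pooled test.

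**Which pooled models are affected.**

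| Pooled endpoint | SAP steps | Contains polyp subjects | Polyp term |
|---|---|---|---|
| Exacerbation frequency, all | 2, 11 | Yes | Not named |
| Exacerbation frequency, no polyps | 3, 12 | No | Constant, cannot be fitted |
| Week 4 CSNS, prior steroid users | 4, 13 | Yes | Not named |

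**Size of the gain.** The documents do not give 3205's size, its polyp share, the prognostic effect of polyps or the exacerbation rates. Everything below is therefore an assumed range.

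*(a) CSNS, treated as a linear model at one time point.* Let f be 3205's share of the pooled data, p the polyp share in 3205, and e the polyp effect in residual SDs. The share of residual variance removed is R² = f·p·(1−p)·e², and the SE is multiplied by √(1−R²). Power from an 80% base becomes Φ[(1.960 + 0.842)/√(1−R²) − 1.960]. The ranges use f = 0.5 to 0.7 and p = 0.3 to 0.5.

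| e | R² | SE reduction | 80% power becomes |
|---|---|---|---|
| 0.2 | 0.0042 to 0.0070 | 0.2% to 0.4% | 80.2% to 80.3% |
| 0.5 | 0.0262 to 0.0437 | 1.3% to 2.2% | 81.0% to 81.7% |
| 0.8 | 0.0672 to 0.1120 | 3.4% to 5.8% | 82.7% to 84.5% |

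Lower end for e = 0.5: 0.5 × 0.3 × 0.7 × 0.25 = 0.0262, and √0.9738 = 0.987.

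*(b) Negative binomial, all pooled subjects.* Information per subject with the term is f·Σwⱼμⱼ/(1+kμⱼ) + (1−f)·m/(1+km). Here μⱼ are the two polyp-stratum means in 3205, wⱼ their shares, m the overall mean and k the dispersion. Without the term it is approximately m/(1+k′m), where k′ is k enlarged by the between-stratum variance. The SE ratio is the square root of the information ratio. Assumptions: f = 0.6, p = 0.5, 0.3 to 1.0 events per year, k = 0.5 to 1.0, 24 weeks of follow-up.

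| Polyp rate ratio | SE reduction | 80% power becomes |
|---|---|---|
| 1.25 | 0.05% to 0.15% | 80.0% to 80.1% |
| 1.5 | 0.2% to 0.5% | 80.1% to 80.4% |
| 2.0 | 0.4% to 1.3% | 80.3% to 81.0% |

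*(c) Simulation check of (b).* The setting was 220 subjects from 3205 (45% with polyps) and 140 from 3206 in the two compared arms, dispersion 1, placebo rate 0.35 per subject, treatment rate ratio 0.6, and 400 simulated trials per setting. Power is the normal approximation Φ(0.511/SE − 1.96), where 0.511 = −ln 0.6.

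| Polyp rate ratio | Mean SE without / with term | SE reduction | Power without / with |
|---|---|---|---|
| 1.5 | 0.2226 / 0.2215 | 0.5% | 63.1% / 63.5% |
| 2 | 0.2158 / 0.2132 | 1.2% | 65.8% / 66.9% |
| 3 | 0.2094 / 0.2029 | 3.1% | 68.4% / 71.1% |

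The two approaches agree: well under 1% at a rate ratio of 1.5 and about 1% at 2. A 3% cut needs a rate ratio of 3, which nothing in the documents supports.

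**The case against.** **The omission may not be final.** The ISE SAP is to describe the pooled endpoints in full, and it was not supplied. SAP section 2 also makes the 3205 SAP the main reference for methods, and its models carry the polyp term. The plural reference to primary models in the negative binomial sentence could even be read to include 3205's. This stands. It shows that the text is silent or ambiguous, not that the term is certain to be missing. It does not remove the case for stating the term, since Protocol 9.5 already sets out a model and the SAP reports no deviation from the protocol.

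**SAP 5.1 does not strip the term from pooled models.** A reader might infer that it does. Its removal is worded for 3206 endpoints and justified by 3206's population, so it does not reach pooled data either way.

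**The gain is too small to matter.** Under weak to moderate assumptions this is largely right. A reader might also infer that the omission endangers the whole testing sequence. That exposure comes from the fixed order of tests, and 0 to 2 points of power at two steps hardly changes it.

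**Bias or an inflated error rate.** A reader might suspect either. Allocation in 3205 was balanced on polyp status by design, and in a linear model leaving out a stratification factor tends to make the test conservative. The documents support neither charge.

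**Prior-year exacerbations as a further covariate.** Protocol 7.1.2 collects the "number of exacerbations in the previous year", and a reader might want it in the negative binomial model too. The documents do not support adding that here. They give no figure for its prognostic value and do not say that it follows the on-study exacerbation definition in Protocol 7.2. The amendment 4.0 summary describes 3205 as completed, so a new covariate would raise a prespecification question. Polyp status is already in 3205's models and is on a different footing.

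**Conclusion.** The point holds as a low-severity, free improvement. As Protocol 9.5 and the synopsis stand, two of the three pooled key secondary models include polyp subjects but do not name polyp status, and the study effect cannot stand in for it. The third model needs no polyp term and would gain nothing from one.

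With weak to moderate polyp effects (up to about 0.5 SD on CSNS, or a rate ratio up to 2), the SE falls by roughly 0.05% to 2%, worth about 0 to 2 points of power. A strong effect of 0.8 SD on CSNS would give up to about 6% and 4.5 points. These sizes rest wholly on assumed values for 3205's size, polyp share, polyp effect and event rates. The benefit is slightly better precision and an unambiguous analysis by the randomised strata. If the ISE SAP already includes the term, what remains is to bring the protocol into line with it.

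**What to change.** - In Protocol 9.5 and the synopsis, and consistently in the ISE SAP, add baseline polyp status (absent, present) to the pooled CSNS model and to the pooled negative binomial model for all subjects. Alongside the study effect this is equivalent to one three-level factor: 3205 with polyps, 3205 without polyps, 3206.
- State that the pooled no-polyp model has no polyp term.
- Add a sentence to SAP 5.1 that the removal applies to models fitted to 3206 alone.

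The cost is wording and one model term. Polyp status was a randomisation stratum in 3205 and is fixed by the entry criteria in 3206, so no new data are needed. The change should be dated before 3206 is unblinded.
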